4.4.1 Type I Error Control Plan

The fixed-sequence testing procedure ([Westfall and Krishen, 2001](#)) will be used to control the overall type I error rate for statistical testing of the primary and key secondary efficacy endpoints.

Contingent upon statistical significance in the primary efficacy endpoint—annualized rate of decrease in percentage of predicted FVC over 52 weeks, the key secondary endpoints will be tested at a two-sided significance level of 5% in the order as shown below:

- Time from randomization to death from any cause
- Annualized rate of decrease in percentage of predicted DL_{CO} over 52 weeks
- Time from randomization to first respiratory-related hospitalization
- Time from randomization to first acute exacerbation or death from any cause
- Annualized rate of change in the ATAQ-IPF total score over 52 weeks
- Annualized rate of decrease in 6MWT distance over 52 weeks
- Time from randomization to first occurrence of a $\geq 15\%$ absolute decrease in percentage of predicted DL_{CO} or death from any cause
- Time from randomization to first occurrence of a $\geq 10\%$ absolute decrease in percentage of predicted FVC or death from any cause
- PFS defined as time to all-cause death, all-cause hospitalization or $\geq 10\%$ relative decrease in FVC (L), whichever occurs first

If a test is not significant at 0.05 level, then the subsequent test(s) will not be considered significant regardless of the associated p-value(s).

4.4.2 Primary Efficacy Endpoint

The primary endpoint is annualized rate of decrease in percentage of predicted FVC through Week 52, which will be compared across treatment arms with use of a random slope model on observed cases at a 0.05 two-sided significance level.

The statistical model is as follows:

$$FVC_{ijk} = (\beta_0 + \beta_{0k}) + (\alpha_i * \beta_1 + \beta_{1k}) * t_k + \eta_k + \epsilon_{ijk}$$

where FVC_{ijk} is the predicted FVC for kth patient at visit j in treatment group i; β_0 is the intercept; α_i and β_1 is the interaction term of the treatment effect ($i = \text{lebri or placebo}$) and the slope; t_k is assessment time (continuous in year) for patient k; η_k is the effect of baseline lung function (defined as $FVC < 50\%$ vs. 50% to 75% vs. $> 75\%$ predicted) for the kth patient; β_{0k} and β_{1k} are the random components for intercept and slope; ϵ_{ijk} is the random error for kth patient at time j; β_{0k} , β_{1k} , and ϵ_{ijk} are assumed to be independent and normally distributed with mean 0 and variance of σ_0^2 , σ_1^2 , and σ_ϵ^2 respectively.

Of note, because of a relatively large number of strata defined by the randomization stratification factors, the analysis will be adjusted for baseline lung function only because baseline FVC may impact the clinical disease course.

From the model, least squares means for the annualized rate of decrease in each treatment arm and the difference between the two treatment arms will be provided with

95% CIs. The model implicitly imputes missing data based on an individual's estimated rate of worsening of lung function prior to study visit discontinuation (i.e., assuming missing at random).

There are several different approaches to summarizing the treatment effect which are ways of understanding the results rather than independent endpoints. For summarizing treatment effect the following will be provided but not considered as separate endpoints or hypotheses.

- Change from baseline to landmark visit time expressed as absolute and relative difference
- Difference in annual rate of decrease expressed as absolute and relative difference
- Categorical absolute change from baseline to each visit time with categories of decrease of $\geq 10\%$ or death before the visit, decrease of 10% to $>0\%$, stability or improvement of change $\geq 0\%$

Change from baseline in percentage of predicted FVC at Week 52 will be analyzed as a sensitivity analysis with use of a mixed-effects model for repeated measures (MMRM) on observed cases at a 0.05 two-sided significance level.

The statistical model is as follows:

$$\text{Chg}_{ijk} = \beta_0 + \alpha_i * \beta_j + \eta_k + \varepsilon_{ijk}$$

where Chg_{ijk} is the change in percentage of predicted FVC for k th patient at visit j in treatment group i ; β_0 is the intercept; $\alpha_i * \beta_j$ is the interaction term of the treatment and categorical visit effect ($i = \text{lebri or placebo}$, $j = \text{Weeks 1, 4, 12, 24, 36, 44, and 52}$; $\alpha_{\text{placebo}} * \beta_{12} = 0$); η_k is the effect of baseline lung function (defined as $\text{FVC} < 50\%$ vs. 50% to 75% vs. $> 75\%$ predicted) for the k th patient; ε_{ijk} is the random error for k th patient at time j and is assumed to be independent and normally distributed with mean 0 and unstructured variance-covariance V . If this analysis fails to converge, analyses using compound symmetry or first order autoregressive structures as alternatives will be investigated.

From the model, least squares means for the absolute change from baseline as well as placebo corrected absolute changes with 95% CIs for each treatment arm at each post-baseline visit will be estimated.

Other sensitivity analyses using various imputation/analysis strategies will also be performed. See Section 4.4.5 for details.

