6.4.1 Primary Efficacy Endpoint

The primary efficacy endpoint is *annualized rate of decrease in percentage of predicted FVC (% FVC/year) through Week 52.*

The annualized rate of decrease in percentage of predicted FVC will be compared across the treatment arms with the use of a random slope model on observed cases at a 0.05 two-sided significance level.

The statistical model is as follows:

$$FVC_{ijk} = (\beta_0 + \beta_{0k}) + (a_i * \beta_1 + \beta_{1k}) * t_k + \eta_k + \varepsilon_{ijk}$$

where FVC_{ijk} is the predicted FVC for k th patient at visit j in treatment group i ; β_0 is the intercept; a_i and β_1 is the interaction term of the treatment effect ($i = \text{lebrikizumab or placebo}$) and the slope; t_k is the assessment time (continuous in year) for patient k ; η_k is the effect of baseline lung function (defined as $FVC < 50\%$ vs. 50% to 75% vs. $> 75\%$ predicted) for the k th patient; β_{0k} and β_{1k} are the random components for intercept and slope; ε_{ijk} is the random error for k th patient at time j ; β_{0k} , β_{1k} and ε_{ijk} are assumed to be independent and normally distributed with mean 0 and variance of σ_0^2 , σ_1^2 and σ_ε^2 respectively.

Note that because of a relatively large number of strata defined by the randomization stratification factors, the analysis will be adjusted only for baseline lung function because baseline FVC may impact the clinical disease course.

From the model, least squares means for the annualized rate of decline in each treatment arm and the difference between the two treatment arms will be provided with 95% CIs. The model implicitly imputes missing data on the basis of a patient's estimated rate of worsening of lung function prior to the study visit discontinuation (i.e., under the assumption that it is missing at random).

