2.3 DETERMINATION OF SAMPLE SIZE

Cohort A

Approximately 150 patients were to be enrolled. A sample size of 75 patients in each treatment group would provide over 85% power to detect a mean change from baseline in percentage of predicted FVC at 52 weeks from 6.6% to 3.0% (a 3.6% absolute difference or 54% relative reduction) under the assumption that the common standard deviation is 7% (as reported in the placebo group in the PIPF-016 [ASCEND] trial of pirfenidone). Power was estimated with use of a two group t-test at a 0.05 two-sided significance level.

A sample size of 75 patients in each treatment group will provide approximately 80% power to detect a change in the annualized rate of decrease in percentage of predicted FVC over 52 weeks from 7.2% to 3.5% (a 3.7% absolute difference or 51% relative reduction) under the assumption that the common standard deviation is 8% (as reported in the placebo group in the ASCEND trial of pirfenidone). Power was estimated with use of a two group t-test at a 0.05 two-sided significance level.

Cohort B

Approximately 330 patients were to be enrolled. A sample size of 165 patients in each treatment group would provide over 85% power to detect a mean change from baseline

in percentage of predicted FVC at 52 weeks from 3.7% to 1.3% (a 2.4% absolute difference or 64% relative reduction) under the assumption that the common standard deviation is 7% (as reported in the pirfenidone group in the ASCEND trial of pirfenidone). Power was estimated with use of a two group t-test at a 0.05 two-sided significance level.

A sample size of 165 patients in each treatment group will provide approximately 80% power to detect a change in the annualized rate of decrease in percentage of predicted FVC over 52 weeks from 4.1% to 1.6% (a 2.5% absolute difference or 60% relative reduction) under the assumption that the common standard deviation is 8% (as reported in the pirfenidone group in the ASCEND trial of pirfenidone). Power was estimated with use of a two group t-test at a 0.05 two-sided significance level.

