3. STUDY CONDUCT

3.1 RANDOMIZATION

Patients were randomized to the treatment arms through the interactive voice/Web-based response system (IxRS). After written informed consent is obtained, patients received a screening number, which was assigned by the IxRS. Following completion of the screening period and after all patient eligibility requirements were confirmed on Day 1, patients were to be assigned an identification number (a different number from the screening number) and randomized in a 1:1 ratio to one of two treatment arms for the 52-week placebo-controlled study period:

- **Cohort A** - lebrikizumab 250 mg SC or placebo SC every 4 weeks
- **Cohort B** - lebrikizumab 250 mg SC every 4 weeks and pirfenidone \leq 2403 mg/d or placebo SC every 4 weeks and pirfenidone \leq 2403 mg/d

Patients were to be randomized on the same day that treatment was to be initiated (Day 1/Visit 2).

Dynamic hierarchical randomization was performed centrally and stratified by the following factors:

- **Cohort A:** region (United States, Europe/Canada, other), lung function (FVC < 50%, 50% to 75%, > 75% predicted), and serum periostin concentration (< 50 ng/mL, ≥ 50 ng/mL)
- **Cohort B:** region (United States, Europe/Canada, other), lung function (FVC < 50%, 50% to 75%, > 75% predicted), and serum periostin concentration (< 50 ng/mL, ≥ 50 ng/mL). Although in the protocol amendment version 6 (2 December 2015) the region strata was to be replaced by prior perfenidone exposure but due to faster than anticipated accrual and logistic challenges this change was not implemented.

During the placebo-controlled study period and the open-label lebrikizumab treatment period, IxRS assigned study treatment kits for patients in Cohort A. During the placebo-controlled study period, IxRS will assign study treatment kits and pirfenidone treatment kits for patients in Cohort B. At each dosing visit during the placebo-controlled period, study and/or pirfenidone treatment kits will be distributed for administration. The placebo and active kits are filled and packaged to look identical. Patient randomization and treatment kit assignments will be verified on an ongoing basis by an external and independent statistical coordinating center to ensure that randomization and kit assignments are conducted correctly by IxRS.

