The dynamic randomization scheme was employed with a biased-coin assignment whenever an imbalance at a given hierarchical level exceeds pre-specified thresholds. The dynamic randomization parameters (i.e., the allocation probabilities and the imbalance thresholds that lead to a biased-coin assignment at each level) will be provided in the Clinical Study Report (CSR).

Patients, all study site personnel, and the Sponsor and its agents (with the exception of the IxRS service provider, the external independent statistical coordinating center responsible for verifying patient randomization and study treatment kit assignments, PK/PD laboratory personnel, and the iDMC, iDCC, and IMC members) will be blinded to treatment assignment for each cohort until the unblinding for each primary analysis.

If unblinding is necessary for patient management (in the case of a serious adverse event [SAE]), the treatment code is available to the investigator through the IxRS. Treatment codes are not to be disclosed except in emergency situations. If the investigator wishes to know the study treatment assignment for any other reason, he or she is to contact the Medical Monitor directly. The investigator should document and provide an explanation for any premature unblinding (e.g., accidental unblinding or unblinding because of a SAE).

As per health authority reporting requirements, Roche will break the treatment code for all unexpected SAEs (see protocol) that are considered by the investigator to be related to study drug.

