4.4 EFFICACY ANALYSIS

All efficacy analyses will be performed on the Randomized Population. Unless otherwise specified, data collected during the 52-week placebo-controlled period will be used, regardless of whether the patient remained on treatment or discontinued the study drug early (but remained in the study). Analyses will be performed for Cohort A and Cohort B separately. For hypothesis testing, each cohort will be considered as a separate study and no type I error control will be done across the two cohorts.

For change-from-baseline endpoints, the baseline value will be defined as the measurement at randomization (Visit 2). If the randomization value is not available, the screening (Visit 1) value can be used in its place (last measurement prior to Day 1). For each subject, relative and absolute changes from baseline will be defined as follows:

- Absolute change from baseline = (post-baseline value – baseline value)
- Relative (%) change from baseline = $100 * (\text{post-baseline value} - \text{baseline value}) / (\text{baseline value})$

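### The primary slope model lets baseline lung function shift only the level and sets the intercept-slope correlation to zero, so its adjustment cannot act on the tested rate of decline: a minor loss of efficiency that the documents do not allow one to size

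*Combined protocol and SAP*

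**What the plan says.** Protocol 6.4.1 and SAP 4.4.2 give the same model. Percent predicted FVC equals a fixed plus a random intercept, plus a treatment-specific slope and a random slope multiplied by time, plus a three-category baseline lung-function effect (below 50, 50 to 75, above 75% predicted), plus error. The lung-function effect is not multiplied by time. The random intercept, random slope and error "are assumed to be independent and normally distributed with mean 0", with three variances and no covariance.

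On covariates, SAP 4.4.2 says that "the analysis will be adjusted for baseline lung function only because baseline FVC may impact the clinical disease course". Protocol 6.4.1 words the choice almost as the SAP does: "the analysis will be adjusted only for baseline lung function because baseline FVC may impact the clinical disease course". The reason given for leaving out the other factors is that the stratification variables define too many strata. SAP 3.1 lists those variables: "Dynamic hierarchical randomization was performed centrally and stratified by the following factors", namely region, lung function and serum periostin. A biased coin is used only "whenever an imbalance at a given hierarchical level exceeds pre-specified thresholds".

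SAP 4.4.2 does not say whether the Week 0 FVC is one of the responses. SAP 4.4 does not settle it either: "For change-from-baseline endpoints, the baseline value will be defined as the measurement at randomization (Visit 2"), which covers change endpoints only.

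**The concern.** The tested quantity is a difference in slopes, and the stated reason for adjusting is an effect of baseline FVC on disease course. Course over time is slope, yet the adjustment enters only the level. With the intercept-slope correlation also set to zero, no baseline covariate and no correlation can sharpen the slope contrast.

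The strata argument fits the 3 x 3 x 2 = 18 crossed cells. It does not rule out separate main effects for region and periostin, which need 2 + 1 = 3 degrees of freedom, or six once their by-time terms are added.

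At stake is the precision of the test that opens the fixed-sequence hierarchy in SAP 4.4.1. Information collected for randomization is not used where it could help.

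**Working it through.** **Plan's own figure.** SAP 2.3 uses an unadjusted two-group t-test at two-sided 0.05. Cohort A (75 per arm, difference 3.7, SD 8) gives 80.3%. Cohort B (165 per arm, "from 4.1% to 1.6% (a 2.5% absolute difference or 60% relative reduction"), SD 8) gives 80.8%. Both match approximately 80%. The calculation takes no credit for covariates or correlation, so what follows measures a gain not taken.

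**Inputs.** From the documents: n, effect and SD as above; spirometry at Weeks 0, 1, 4, 12, 24, 36, 44 and 52 (schedules of assessments). With weeks divided by 52, the mean time is t = 173/416 = 0.416 and Sxx = 1.084. Assumed: intercept SD s0, residual SD se, correlation r, no dropout. Total variance of a patient's fitted slope is held at 64, so the between-patient slope variance is s1^2 = 64 - se^2/Sxx.

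**Formula.** For each patient's least-squares intercept and slope:
- S00 = s0^2 + se^2(1/8 + t^2/Sxx)
- S01 = r s0 s1 - se^2 t/Sxx
- S11 = 64

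The arms share a fixed intercept. The slope contrast is therefore the difference in mean slopes minus L times the difference in mean intercepts, with variance (2/n)(S11 - 2 L S01 + L^2 S00). A free covariance uses L = S01/S00. The SAP model uses the value for r = 0, which is L = -(se^2 t/Sxx)/S00.

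**Worked case:** s0 = 7, se = 2.5, r = 0.3, n = 165.
- s1^2 = 64 - 6.25/1.084 = 58.24, so s1 = 7.631 and r s0 s1 = 16.03.
- S00 = 49 + 6.25 x 0.2845 = 50.78. S01 = 16.03 - 2.40 = 13.63.
- SAP model: L = -2.40/50.78 = -0.047. Variance term 64 + 1.29 + 0.11 = 65.40. SE = sqrt(2 x 65.40/165) = 0.890. Power = Phi(2.5/0.890 - 1.96) = 0.802.
- Free covariance: 64 - 13.63^2/50.78 = 60.34. SE = 0.855. Power = 0.832.
- Gain: about 3 points. SE ratio 0.890/0.855 = 1.04.

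**Range, free covariance alone** (s0 6 or 13, se 2 or 3, either sign of r, Week 0 as a response or not; that last choice moves the gain by less than 0.25 points):

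| absolute r | gain, power points | excess variance of SAP model |
|---|---|---|
| 0 | 0 | 0 |
| 0.1 | 0.3-0.4 | 0.7-0.9% |
| 0.2 | 1.1-1.5 | 3.0-3.9% |
| 0.3 | 2.5-3.3 | 6.8-9.3% |
| 0.5 | about 7-9 | not tabulated; SE 9-14% larger with s0 7 or 12, se 2.5 or 4 |

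Up to 0.3 the SAP model's own power stays at 0.795-0.835. At 0.5, on the s0 7 or 12 and se 2.5 or 4 grid, it is 0.784-0.853. Its type I error is 0.050 throughout.

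**Factor-by-time terms alone.** If factors explain 2, 5 or 10% of between-patient slope variance, the gain is 0.5, 1.1-1.3 or 2.2-2.5 points when the factors are perfectly balanced. With chance balance only it is 0.7, 1.6-1.8 or 3.3-3.7. Under perfect balance the SAP model is slightly conservative (type I error 0.048, 0.045, 0.039-0.041).

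**Both together.** The two changes overlap, so their gains must not be added. With slope linear in baseline FVC over the eligible 40-100% range, lung-function category by time plus a free covariance gains about 0.2-0.3, 0.9-1.1 and 2.1-2.5 points at correlations of 0.1, 0.2 and 0.3.

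**In patients.** t-test power is 0.808 at 165 and 0.819 at 170 per arm, so one point is worth about 4-5 patients per arm. Protocol 9.3 reports 507 enrolled and Protocol 5.1.1.1 gives 78 + 76 = 154 treated in Cohort A. That leaves about 353, or 176 per arm, where t-test power is already 0.832.

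**Dropout.** In large-sample simulations with data missing at random, similar dropout (20-23%) moved the contrast from the fuller model by about 0.02 points per year or less. With 31% against 10% dropout and no true difference, the shift was about 0.05 at a correlation of 0.3. It was about 0.14-0.17 at 0.5 combined with a baseline effect on slope. Against the planned 2.5 these are 2% and about 6-7%.

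**The case against.** The strongest case is that this is a valid, prespecified model that meets its stated power, and that every gain rests on inputs the documents do not give. That stands. A reader might infer that the power is overstated or that the primary test is invalid. Neither is supported: power was computed without these terms, and complete-data type I error is at or below nominal.

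Second, other analyses relax the restrictions. The MMRM puts lung-function category on the change scale with unstructured covariance (SAP 4.4.2), the rank ANCOVA is stratified by it (SAP 4.4.5), and SAP 4.4.6 examines region, baseline FVC and periostin. This stands in part. The first two are sensitivity analyses and the third concerns effect modification. In the MMRM the category is not crossed with visit, so it shifts change equally at Week 1 and Week 52.

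Third, parsimony. Region and periostin main effects alone would also shift only the level, so acting on slope takes six parameters. No text ties region to slope, and Protocol 1.3 reports a periostin correlation without an effect size. This stands, so those terms are optional.

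Fourth, timing. SAP Version 2 was signed on 13 September 2017, after the Cohort A results and an unplanned Cohort B futility look, and the Internal Monitoring Committee text is redacted. This stands, so any change to the primary model must be conditional.

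**Conclusion.** The structural point holds in both documents: the chosen adjustment cannot act on the rate of decline, which is what its stated reason concerns. It is a minor efficiency point. If the correlation is at most about 0.3 in absolute value, the two core changes together are worth up to about 2.5 power points, and a free covariance alone up to 3.3 when the correlation lies wholly within lung-function category. At 0.5 the loss is no longer small. These figures assume slope SD 8, 165 per arm and complete data.

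Three further inferences should be resisted. First, that precision is the only possible cost: strongly unequal dropout can add a small bias. Second, that the gain has a ceiling. For a single two-group factor, the slope gap passes the assumed control decline of 4.1 at about 7-7.5% of slope variance. But nothing excludes a larger gap, and three independent factors at 5% each total 15% with gaps of about 3.5. Third, that baseline FVC plays no part at all: if Week 0 is a response, it enters the fitted slopes as an outcome.

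**What to change.** For Cohort B, in SAP 4.4.2 and before unblinding:
- Add lung-function category by time.
- Use an unstructured 2x2 covariance for the random intercept and slope, with the present independent structure as the stated fallback on non-convergence. The MMRM already has such a rule: "If this analysis fails to converge, analyses using compound symmetry or first order autoregressive structures as alternatives will be investigated".
- Optionally add region and periostin category with their by-time terms, stating that the documents do not link region to slope.
- State whether Week 0 FVC is a response.
- Keep the current model as a named sensitivity analysis.

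Make this the primary model only if the sponsor documents that those making the change had no access to Cohort B interim results. Otherwise leave the primary model alone and add the fuller model as a labelled sensitivity analysis. Do the same for Cohort A, which is already unblinded.

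Cost: a further SAP amendment and no new data. The core change adds three parameters (two for category by time, one covariance). The optional terms add six (region 2 + 2, periostin 1 + 1), making nine against roughly 330-353 patients. If the primary model changes, the two cohorts will have different primary models, and the change will post-date the Cohort A results and the futility look. Both should be stated in the report.

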4.4.4 Exploratory Efficacy Endpoints

Time-to-Event Endpoints

These endpoints will be analyzed and summarized with use of the same methods for the time-to-event secondary endpoints.

Change-from-Baseline Endpoints

These endpoints will be analyzed and summarized with use of the same methods as the endpoint—change from baseline in percentage of predicted FVC in Section 4.4.2.

Annualized Rate of Decrease Endpoints

The annualized rate of decrease in SpO₂ (%) over 52 weeks will be analyzed and summarized with use of the same method as for the annualized rate of decrease in percentage of predicted FVC.

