4.4.6 Subgroup Analyses

Subgroup analyses will be performed to assess the impact of select baseline characteristics (see [Table 1](#)) on the change from baseline in percentage of FVC at 52 weeks, by examining the interaction with the study drug with use of the MMRM model. Each baseline factor will be analyzed separately. Some categories may be grouped to allow sufficient sample size for interpretation.

Table 1 Subpopulation Definitions

Baseline Characteristics	Categories
Geographic region	U.S. ROW
Age at randomization	< 65 years ≥ 65 to < 75 years ≥ 75 years
Sex	Female Male
Race/ethnicity	White Nonwhite
Time from IPF diagnosis to randomization	< 1 year ≥ 1 year
Baseline %FVC	< 55% predicted 55% to < 75% predicted ≥ 75% predicted
FEV ₁ /FVC	< 0.80 ≥ 0.80
Hgb-corrected DL _{CO} (% predicted) ^a	< 35% 35% to < 50% ≥ 50%
GAP Index (see Appendix 6)	I/II or III
Extent of fibrosis on HRCT at baseline, expressed as a QLF score	Divided at the median for initial summary score
Periostin	< 50 ng/mL ≥ 50 ng/mL
Duration of prior pirfenidone exposure (for Cohort B only)	0 (started after informed consent) < 1 year ≥ 1 year

FEV₁=forced expiratory volume in 1 second; FVC=forced vital capacity;
HRCT=high-resolution computed tomography; QLF=quantitative lung fibrosis; ROW=rest of world.

Note: Hispanic/Latino ethnicity grouped with nonwhite for subgroup analyses.

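### The change-from-baseline MMRM has no own-baseline covariate, which costs precision for DLCO, SGRQ, ATAQ-IPF and Borg changes and little for % predicted FVC

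*Combined protocol and SAP*

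**What the plan says.** SAP 4.4.2 makes the random slope model the primary analysis. Change in % predicted FVC at Week 52 "will be analyzed as a sensitivity analysis with use of a mixed-effects model for repeated measures (MMRM"), run "on observed cases at a 0.05 two-sided significance level". The response is the change score. The fixed effects are an intercept, treatment by categorical visit (Weeks 1, 4, 12, 24, 36, 44 and 52) and one patient-level term, which "is the effect of baseline lung function (defined as" FVC below 50%, 50% to 75%, or above 75% predicted). The model has no continuous baseline and no baseline-by-visit term.

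The model is then reused:

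- SAP 4.4.4: exploratory change-from-baseline endpoints "will be analyzed and summarized with use of the same methods as the endpoint" just described. SAP 2.2.3 lists Borg CR10, ATAQ-IPF and SGRQ changes among them.
- SAP 4.4.5, analysis D: change in % predicted FVC and in % predicted DLCO, with deaths imputed.
- SAP 4.4.6: subgroup effects on FVC change are assessed "by examining the interaction with the study drug with use of the MMRM model".

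The only stated reason for the choice of covariates is given with the random slope model. The stratification factors define many strata, so "the analysis will be adjusted for baseline lung function only because baseline FVC may impact the clinical disease course".

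**The concern.** A change score contains the baseline with a negative sign. Measurement error in the baseline therefore makes change and baseline negatively correlated: a patient whose baseline reads high by chance tends to show a larger fall. If baseline is in the model, that part of the noise is removed and a chance difference between arms at baseline is corrected. If it is not, the noise stays in the standard error and part of the imbalance stays in the estimate.

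An FVC category is a coarse version of the right covariate when the outcome is FVC. When the outcome is DLCO, a questionnaire score or Borg dyspnea, it is a different variable. Randomization (SAP 3.1) balances region, FVC category and periostin, and none of these other baselines. At stake is the precision of one sensitivity analysis for DLCO and of three exploratory outcomes.

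**Working it through.** **1. The plan's own figures.** SAP 2.3 gives, for Cohort A, "A sample size of 75 patients in each treatment group would provide over 85% power" for "a 3.6% absolute difference or 54% relative reduction" with SD 7. With power = Phi(difference / (SD x sqrt(2/n)) - 1.96):

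- Cohort A: 3.6 / (7 x sqrt(2/75)) = 3.6 / 1.143 = 3.15, giving 88.3% (87.9% with the noncentral t).
- Cohort B (165 per arm, 2.4, SD 7): 2.4 / 0.771 = 3.11, giving 87.6% (87.4%).

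Both agree with the stated figure of over 85%. The plan's power therefore reproduces without any covariate.

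**2. Outcomes whose own baseline is missing (DLCO, SGRQ, ATAQ-IPF, Borg).** Let baseline and follow-up have equal variance S² and correlation rho. Then:

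- Variance of change = 2S²(1-rho).
- Residual variance after adjusting for baseline = S²(1-rho²).
- Ratio, unadjusted to adjusted = 2/(1+rho); proportion of variance saved = (1-rho)/2.
- A chance baseline difference d shifts the expected difference in change by -(1-rho)d. If d is one standard error, S x sqrt(2/n), the shift in units of the unadjusted standard error is (1-rho)/sqrt(2(1-rho)) = sqrt((1-rho)/2).

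| rho (assumed) | Variance saved | Excess variance if unadjusted | Power if the adjusted analysis has 80% | Shift from a 1-SE imbalance |
|---|---|---|---|---|
| 0.9 | 5% | 5% | 78% | 0.22 SE |
| 0.8 | 10% | 11% | 76% | 0.32 SE |
| 0.6 | 20% | 25% | 71% | 0.45 SE |

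These figures treat the FVC category as uninformative about the outcome's own baseline. To the extent that it is informative, for instance for DLCO, the saving is smaller.

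**3. If true change differs between patients.** Suppose each patient's true change varies independently of baseline. Let r be the reliability of a single measurement, D² the variance of true change and E² the error variance. The saving is E²(1-r)/(D² + 2E²). With D = 0 this is (1-r)/2. If half the variance of change is real (D² = 2E²), it is (1-r)/4: 2.5%, 5% and 10% at r = 0.9, 0.8 and 0.6.

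**4. % predicted FVC.** The documents give no baseline SD. Assume baseline is normal, truncated to the eligible range of 40-100% predicted, with mean 65-75 and SD before truncation 12-20. Assume also equal variances, so that rho = 1 - (SD of change)²/(2 x baseline variance). Worked case, mean 70 and SD 15:

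- Baseline SD after truncation is 13.2, so rho = 1 - 49/(2 x 13.2²) = 0.859.
- Share of change variance explained by continuous baseline: (1 - 0.859)/2 = 0.070.
- The three categories capture 0.76 of the baseline variance, hence 0.76 x 0.070, about 0.054.
- Variance ratio, category to continuous: (1 - 0.054)/(1 - 0.070), about 1.02.
- Cohort A power: 87.9% with no adjustment, 89.6% with the category, 90.1% with continuous baseline.

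Over the full range, which takes both SAP SDs (7 for change, 8 for annualized rate), the categories capture about 70-81% of baseline variance. The variance ratio is 1.01-1.04, and power rises by about 0.3-1.5 points. The upper end uses SD 8: with mean 75 and SD 12 the ratio is 1.031 at SD 7 and 1.042 at SD 8. A one-standard-error baseline imbalance shifts the FVC difference by 0.08-0.25 points with the category, against 0.18-0.46 with no adjustment, so about half of the effect is already removed.

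**The case against.** The strongest reply is that nothing confirmatory depends on this model. SAP 4.4.2 calls it a sensitivity analysis, and no change-from-baseline test appears in the fixed sequence of SAP 4.4.1. The hierarchy's DLCO, ATAQ-IPF and 6MWT endpoints use the random slope model, and the secondary SGRQ endpoint is a time to event. All of that stands. A reader might infer from the missing covariate that the primary result is compromised or the estimates biased; the documents support neither. Under randomization, leaving out a baseline covariate costs precision and leaves the realized chance imbalance in place, without systematic bias.

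A reader might also infer that FVC change is not adjusted for its own baseline at all. That is wrong: the category is baseline FVC in coarse form, and randomization is stratified on the same cut points in both cohorts. Nor can the point be extended to the QLF score or the biomarkers, because SAP 2.2.3 sends HRCT and biomarker analyses to a separate document.

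Three further objections hold in part:

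- The covariate choice was deliberate. But the reason given is the number of strata, and a continuous covariate creates none. SAP 4.4.3 already adds height, sex and age to the model for FVC in mL/year.
- The savings rest on assumed correlations, and real variation in true change reduces them. This is correct, and the halved figures are shown above.
- A baseline-by-visit interaction is more than one coefficient, in a model with an unstructured covariance and a convergence fallback. This is correct, and is counted in the cost.

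**Conclusion.** The point holds in limited form. For DLCO change in analysis D and for the exploratory SGRQ, ATAQ-IPF and Borg CR10 changes, the plan omits the outcome's own baseline, although no change score can be computed without it. The loss is about 5-20% of residual variance for rho between 0.9 and 0.6. It is less if true change varies independently of baseline or if the FVC category predicts the outcome's baseline. For % predicted FVC, including the subgroup analyses, the loss is about 1-4% under assumed baseline distributions, which is minor.

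The result rests on assumed correlations and baseline SDs, equal variances at baseline and follow-up, and no allowance for dropout; the documents supply none of these inputs. The primary random slope test, the fixed sequence and the stated power are not called into question.

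**What to change.** In SAP 4.4.2, add the endpoint's own continuous baseline and its interaction with visit to the MMRM, and keep the FVC stratum term. State that the same applies wherever the model is used in 4.4.4, 4.4.5 analysis D and 4.4.6, each time with the baseline of the outcome being analyzed, as defined in SAP 4.4. Leave QLF and the biomarkers to their separate plan.

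SAP section 1 says that this version was being amended before Cohort B was unblinded, so the term can be pre-specified for Cohort B. Protocol 1.4 records that Cohort A was unblinded in May 2016; there the adjusted model should be labeled supplementary and reported beside the planned one.

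The cost is one coefficient per post-baseline visit. By the schedules of assessments that is seven for FVC and DLCO, five for SGRQ and ATAQ-IPF, and two for Borg. No patient is lost, because the change score already requires the baseline.
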